Study Protocol

Official Title: A Pilot Study: Metformin as an immune and inflammatory modulating therapy in older adults without diabetes.

ClinicalTrials.gov ID (NCT number): NCT03772964

Protocol Date: 5/18/2019

Scientific Background

Metformin is considered first line therapy for patients with DM2 with hyperglycemia that cannot be controlled with life style alone. Unlike other oral medications, metformin is favored for its insulin sensitizing effects resulting in improved glycemic control, weight loss, and overall improvement of metabolic syndrome. Over the past fifteen years, metformin has received significant attention for its other potential therapeutic uses. Metformin has been found to decrease the rate of age related illness progression improving longevity, especially in the setting of cancer. Recent clinical trials across multiple disease states have shown metformin to decrease all-cause mortality in diabetic and non-diabetic patients.^{1–3} Additionally, in both animal models and human trials, metformin has been shown to decrease the risk of arterial and venous thrombosis without affecting bleeding time through its interaction with platelet mitochondria.^{4–6} Furthermore, treatment of diabetics with metformin has been shown to improve cognition.⁷ Although the mechanisms by which metformin effects longevity is an active area of both basic science and clinical research, it clearly has anti-inflammatory properties which are both independent and dependent of glycemic control.⁸ Recently, surgical outcomes have focused on optimizing older, deconditioned patients prior to the operation with varying protocols referred to as prehabilitation. These programs work to improve the body's response to the surgical stress resulting in improved wound healing, decreased postoperative complications, and decreased hospital length of stay. The affect of metformin, like increasing physical activity, has wide spread affects on physiology. We therefore hypothesize that metformin administration to non-diabetic adults will improve clinical outcomes to physiologic stress (including surgical stress) by improving underlying immune and inflammatory responses, that can be deleterious.

The body's response to stress is a complex interplay between the magnitude of the stress and host factors including genetics, epigenetics, age, and lifestyle. Surgical procedures result in a loss of physical barriers to the environment, local tissue injury, vascular damage, altered neurohormonal signaling, and hemodynamic changes.^{9–13} Tissue injury results in stimulation of pattern recognition receptors (PRRs), including Toll-like receptors (TLRs). The systemic level of lipopolysaccharide (LPS), a ligand for TLR4, is increased following major abdominal surgery.^{12–14} LPS stimulation of TLR4 leads to release many pro- and anti-inflammatory cytokines, including TNF- α , IL-1, IL-6, IL-8, and G-CSF, allowing for an appropriate immune response to protect the body from invading pathogens, aid in tissue healing, and allow for overall survival.^{2,3,13} However, the systemic complications of an overwhelming inflammatory response, including but not limited to acute respiratory distress syndrome, acute kidney injury, vascular thrombosis, poor wound healing both due to and independent of glycemic control, deteriorations in memory and mood, and depressed cardiac function are all well-established postoperative complications. The balance of the pro- and anti-inflammatory reaction is key to homeostasis and recovery. However, why some patients suffer from postoperative inflammatory complications while others do not is not well understood. Further, currently there is no established anti-inflammatory treatment in the peri-operative period to help alleviate or prevent an overwhelming pro-inflammatory systemic response. This study will help us to better understand the underlying mechanisms of metformin and potentially identify it as a source of pharmacologic prehabilitaiton improving surgical outcomes.

The underlying mechanisms of action of metformin are under active investigation. Presumably,

cellular mitochondria are thought to be the primary site of metformin activity. Metformin decreases intracellular AMP and increases 5'-AMP-activated protein kinase (AMPK) resulting in three main down-stream effects.¹⁵ First and foremost, there is a decrease in gluconeogenesis, decreasing serum glucose levels, and improving insulin resistance. Secondly, mitochondrial AMPK activation inhibits mechanistic target of rapamycin (mTOR), which decreases mitotic activity and therefore has anti-tumor affects and influences mitochondrial homeostasis. Finally, downstream protein synthesis inhibition results in decreased production of both pro-inflammatory cytokines and reactive oxygen species (ROS) through activation of the thioredoxin antioxidant system decreasing DNA damage.¹⁵⁻¹⁸

In addition to its effects on human cellular mitochondria and systemic inflammation, metformin's direct effect on the gastrointestinal system has become an active area of research. Metformin has been shown to alter activity of the gastrointestinal endocrine system, increasing release of glucagon like peptide-1 (GLP-1) and pancreatic polypeptide (PPY) which regulate bile acids and control satiety and metabolism.^{20,21} Further, metformin controls and altering the abundance of specific bacteria and their response to stimuli.²² These alterations are thought to contribute to both glycemic control and the overall improved diabetic phenotype that results after administration of metformin. However, these positive effects have been minimally explored and are therefore not well understood in the non-diabetic patient.

Recently, there have been multiple prospective clinical trials exploring the effect metformin has in non-diabetic patients. Non-diabetic patients were treated with 250mg - 875mg three times daily or 2000mg daily for 14 days – 48 weeks showing an excellent safety profile. The metformin was very well tolerated with the primary side effect (30-60% of subjects) being self-limited gastrointestinal discomfort including mild diarrhea and anorexia.²³⁻²⁵ Across multiple disease states, metformin has been shown to decrease appetite stimulating GLP-1, decrease low density lipid profiles, decrease the mitotic rate in breast cancer, and improve liver pathology in patients with non-alcoholic steotatic hepatitis.^{1,12,20,23,25,26} As discussed above, some of these changes are attributed to the anti-glycemic and anti-tumor effects of metformin, yet the anti-inflammatory role cannot be underestimated. To our knowledge, there has been no study of the affect metformin has on inflammation, the microbiome, thrombosis, and cellular respiration as it links to physiologic and cognitive changes in non-diabetic patients.

Therefore, we hypothesize that aged non-diabetic subjects treated with a short course of metformin will have a beneficial change in metabolic and immune signaling and gut microbial homeostasis with an improved inflammatory response.

Study Objectives

This is a study examine if metformin improves the immune and inflammatory responses of non-diabetic, older adults.

We will begin to test this hypothesis by examining the following specific aims.

1. To determine the influence of metformin on basic metabolic, coagulation, and hematologic profiles

2. To discover the influence of metformin on physiologic and inflammatory responses in older adults including affects on peripheral blood mononuclear cells (PBMCs) phenotype and ex vivo inflammatory response to innate immune stimuli.
3. To discover the influence of metformin on thrombotic factors and platelet function in an ex vivo model.
4. To determine the influence of metformin on cellular respiration pathways including epigenetics and mitochondrial function.
5. Determine the influence of metformin on physiologic parameters of physical activity including grip strength as measured by a dynamometer and a short physical performance battery.
6. To establish dose specific gastrointestinal changes to the microbiome of metformin.

Study Design & Methods

All samples will be gathered prior to, throughout the 90 days (30, 60 and 90 days), and again approximately 30 days following completion of the metformin exposure.

- 1.) Changes in basic metabolic, coagulation, and hematologic profiles during and following exposure to metformin.
- 2.) Establish dose specific responses to affects on PBMC and ex vivo inflammatory response to innate immune system during and following metformin exposure. Cells will also be assessed for epigenetic changes by Chromatin immunoprecipitation.
- 3.) Understand the dose-specific effects of metformin on thrombotic factors, coagulation, and platelet function in an ex vivo model.
- 4.) Mitochondrial analysis of cellular respiration.
- 5.) Stool samples assessed for changes in the gastrointestinal microbiome

Cognition and physiology will be assessed at the baseline, 90 day, and 120 day time points.

- 6.) Physiologic testing: grip strength as measured by a dynamometer and a short physical performance battery

Unexpected adverse events including significant illness, hospitalization, emergent or urgent surgery or procedure, psychiatric hospitalization or inpatient rehabilitation, would require the study team to discontinue the subject's participation.

Additionally, if the subject fails to participate in the required study procedures they will receive compensation for those items that they have completed. However, they may be removed from the study and not allowed to participate in the study going forward. If participation needs to be discontinued, the study team will make up to 1-5 separate efforts to contact the subject in order to discuss their removal from the study and to instruct them to both discontinue and return the study medication. All unused study medication will be returned to the study pharmacy, IDS.

Eligibility Criteria

List the inclusion criteria:

1. Age ≥ 55 and ≤ 85 years of age
2. Non-diabetic
3. Adjusted risk analysis index (RAI) 20-42
4. Estimated glomerular filtration rate ≥ 45
5. No evidence of hepatic dysfunction on comprehensive metabolic panel
6. No clinical evidence of cardiac failure
7. Existing University of Pittsburgh Medical Center Patients

List the exclusion criteria:

1. Hypersensitivity to metformin or any component of the formulation
2. Acute or chronic metabolic acidosis with or without coma
3. Pregnant or breastfeeding females
4. Evidence or history of hepatic, renal, or cardiac failure
5. Excessive acute or chronic ethanol use
6. Planned or known hospital admission, exposure to anesthesia, or surgical intervention 30 days prior to study or scheduled 30 days after the trial initiation
7. Laboratory analysis showing HbA1c > 6.1 or eGFR < 45 on baseline labs

Statistical Considerations

This prospective randomized control study is powered based upon prior studies our group has completed on the cellular response to inflammation from PBMCs in healthy volunteers. This variable was chosen, as we believe this to be the most impactful variable included in this study. Previously, our group has looked at the immune response to lipopolysaccharide in healthy volunteers PBMCs ex vivo. In this study, we noted a statistically significant increase in pro-inflammatory cytokines between the two groups by approximately 40%. We expect a standard deviation of around 50% of the baseline values. Therefore, based upon previous inflammatory changes seen in healthy volunteers and a desired alpha = 0.05 and a beta = 0.2, our most conservative projected sample size using a two-sided Mann-Whitney test is 25 patients per group. With possible attrition we plan to enroll 30 patients per group. Therefore, across dosing we require a total of 120 patients in order to reach statistical significance. For this trial, we are collecting data in order to pilot a larger trial after we have data from this trial. Therefore, we expect to use the data from these 32 patients to understand how to power a larger study.

Patients will be used as their own controls before, during and after the exposure period, allowing for paired testing. Changes in laboratory venous and stool samples values will be compared using parametric and non-parametric standard statistics, as required. Differences in baseline physiologic testing will be controlled for based on their RAI score and the medical comorbidities, therefore each person serves as their own control. Both the 90 day treatment results and the 120 day test results (30 days after treatment discontinuation) for physiologic

testing will be compared to the individuals baseline values. Additionally, the various treatment doses will be compared at baseline, to ensure randomization allowed for equivalent patient groupings.

Randomization and blinding will be completed by IDS who will be provided with a block randomization scheme (see Sample Randomization in the Supporting Documents Section). The randomization scheme will have a block size of 8. Within each block, the randomization is classic and 1:1:1:1 between groups.

Changes from baseline will be investigated at each time point using ANOVA. Significance will be assumed with $p<0.05$.

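### The 120 patients are sized for one unadjusted two-group test, but the plan analyses four arms by ANOVA with no matching power calculation and no error control for the dose comparisons

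*Combined protocol and SAP*

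**What the plan says.** All the statistical text is in Statistical Considerations of the combined protocol and SAP.

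- **Effect and spread.** Earlier work by the same group in healthy volunteers' PBMCs showed a "statistically significant increase in pro-inflammatory cytokines between the two groups by approximately 40" per cent. For the spread: "We expect a standard deviation of around 50% of the baseline values".
- **Error rates and test.** The calculation uses "a desired alpha = 0.05 and a beta = 0.2", and "our most conservative projected sample size using a two-sided Mann-Whitney test is 25 patients per group".
- **Scaling up.** "With possible attrition we plan to enroll 30 patients per group". Then: "Therefore, across dosing we require a total of 120 patients in order to reach statistical significance".
- **Design.** Blocks of 8, and within each block "the randomization is classic and 1:1:1:1 between groups".
- **Analysis.** "Changes from baseline will be investigated at each time point using ANOVA", with significance at p<0.05.

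The section names no contrast, post-hoc procedure or multiplicity adjustment, and it gives no power for ANOVA. It also allows paired within-patient testing, and parametric or non-parametric methods as needed. The same paragraph calls the trial a pilot and expects data from 32 patients, to be used in powering a larger study. Study Design & Methods frames the PBMC question, which is the variable used for sizing, as one about dose-specific responses.

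**The concern.** The test that was powered is not the test that is named. A two-group calculation gives the chance of detecting one specified difference between two arms. The usual four-arm ANOVA F test spreads its sensitivity over three degrees of freedom, so its power depends on where all four means lie, and the plan does not state that pattern. A significant F test also does not say which dose differs, although the aim is dose-specific. If pairwise comparisons are meant instead, each at 0.05, nothing in the plan holds the overall error rate at 5%.

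At stake is the meaning of the 120. A reader will take it as giving 80% power for the dose comparison. Because the data are meant to inform a larger trial, the same mismatch could be carried forward.

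**Working it through.** **Inputs from the plan.** Difference 40%, SD 50% of baseline, so d = 40/50 = 0.8. Two-sided alpha 0.05, power 0.80. Four equal arms, 25 evaluable and 30 enrolled per arm.

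**Assumptions that the plan does not supply.** The 50% SD is the SD of change. The largest difference between any two arms is 0.8 SD. The pattern of the four means is as listed below.

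**1. The plan's own figure.** n = 2 × (1.960 + 0.842)² / 0.8² = 24.5, rounded up to 25 per group. Power at 25 is 80.7% by the normal approximation. The step to 30 implies attrition of 1 − 25/30 = 16.7%, and 4 × 30 = 120. So 25 is reproduced, as a single unadjusted two-group comparison. Simulated Mann-Whitney power on normal data is slightly lower, 76.5% at 25 per group.

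**2. Overall F test on four arms.** The noncentrality parameter is λ = n × Σ(mᵢ − m̄)², with means in SD units, on 3 and 4(n − 1) degrees of freedom. For equally spaced means Σ = 0.356, so at n = 25 λ = 8.89. The critical F(3, 96) is 2.70 and the power is 68.6%.

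| Arm means (SD units) | λ at 25 | Power, 25 per arm | Power, 30 per arm | Power, 8 per arm |
|---|---|---|---|---|
| 0, 0.27, 0.53, 0.8 (equally spaced) | 8.9 | 68.6% | 77.5% | 23.1% |
| 0, 0.4, 0.4, 0.8 (middle arms halfway) | 8.0 | 63.4% | 72.6% | 21.1% |
| 0, 0.4, 0.8, 0.8 (plateau) | 11.0 | 78.6% | 86.4% | 28.0% |
| 0, 0, 0, 0.8 (one arm differs) | 12.0 | 82.4% | 89.4% | 30.4% |
| 0, 0, 0.8, 0.8 (two against two) | 16.0 | 92.4% | 96.4% | 39.7% |

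The last column is 32/4 = 8 per arm. For 80% power the first two rows need 32 and 36 evaluable per arm (128 and 144 in all). At the implied 16.7% attrition that is 156 and 176 enrolled.

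**3. Pairwise comparisons at 25 per arm.** The test is a t test with pooled SD, noncentrality 0.8 × √(25/2) = 2.83, 96 df.

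- Bonferroni for three comparisons with a reference arm (critical value 2.44): 65%.
- Dunnett (critical value about 2.38): 67%.
- Tukey over all six pairs (critical value 2.61): 59% for one named pair.
- No adjustment: by simulation, the chance of at least one false positive is about 12% for three comparisons with a common arm and 20% for six pairs.

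**4. Sensitivity to the SD.** If the 50% is a cross-sectional SD, with equal variances at both visits, the SD of change is that SD × √(2(1 − r)), where r is the baseline-to-follow-up correlation. It equals the stated SD only at r = 0.5. For the two graded patterns at 25 per arm the F test then has 48–53% at r = 0.3, 74–79% at r = 0.6 and about 87–90% at r = 0.7.

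**5. A linear trend contrast (−3, −1, 1, 3) at 25 per arm.**

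| Arm means | Trend contrast | F test |
|---|---|---|
| Equally spaced | 84% | 69% |
| Only the top arm differs | 76% | 82% |
| 0, 0.8, 0.8, 0.4 | 26% | 79% |
| 0, 0.8, 0, 0 | 14% | 82% |
| 0, 0.8, 0.8, 0 | 5% | 92% |

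**The case against.** The strongest reply is that the plan does not commit to an overall F test. It says only ANOVA, which can include contrasts, and it also provides for paired tests. It gives no dose-response shape, and several shapes give the F test 79–92%. It does not say whether the 50% SD is cross-sectional or of change, and with patients as their own controls the correlation could push power either way. It describes no common control arm in the text available, so the Dunnett figures are conditional. Finally, it calls itself a pilot.

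Much of this stands, and it limits the size of the point. A reader might infer that the trial is known to have only 63–69% power. The documents do not support that: the range belongs to two assumed graded patterns, at 25 evaluable per arm, under one reading of the SD. With all 120 analysed the same patterns give 73–78%.

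A reader might also infer that a trend contrast should replace the ANOVA. That does not follow either. It presupposes arms ordered by dose, which the text does not show, and it loses most of its power if the response is not monotone.

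The core is not answered. On none of these readings does the two-group calculation supply the power of the four-arm analysis. The pilot label does not help, because the same paragraph says that 120 are required to reach significance.

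**Conclusion.** The point holds in a limited form. The 25 per group, 30 with attrition and 120 in total are justified for a single unadjusted two-group comparison of 0.8 SD. They are not justified for the four-arm ANOVA of changes from baseline or for a set of dose comparisons.

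The size of the gap is conditional on the dose pattern and the SD of change. For graded patterns, with the stated SD taken as the SD of change, power falls short of 80% by about 11–17 points at 25 evaluable per arm and by 2–7 points at 30. For some other shapes there is no shortfall. Adjusted comparisons with a reference arm fall short by about 13–15 points per dose at 25.

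The arithmetic is firm. The defect lies in the unspecified primary test and its missing power calculation and error control, not in a known test shown to be underpowered. If the trial enrols 32, the graded F test has about 21–23%, and the sizing argument for 120 has no bearing on it.

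**What to change.** 1. Do not present 120 as giving 80% power for the four-arm analysis.
2. For PBMC cytokine response, name the test and time point that will decide the result. Restate the power for that test, with the assumed dose pattern and the SD of change (or the cross-sectional SD and correlation).
3. Use a multiplicity-adjusted procedure for the dose comparisons: Dunnett if there is a reference arm, otherwise Tukey.
4. Reconcile 120 with 32, and state the power at the size the trial will actually enrol. If that is 32, describe the dose comparison as exploratory.
5. If the arms are ordered by dose, a linear trend contrast may be added as a supplementary analysis beside the ANOVA, not in place of it.

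The cost is protocol wording and a short recalculation; none of these steps needs more patients. More patients would be needed only if the sponsor wants to keep 80% power for graded patterns with the overall F test: 128–144 evaluable under the assumptions above. The price of adjustment is lower power for each single comparison, which the restated figures should show.

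### Statistical Considerations gives two sizes for the same trial, 120 patients (30 per group) and 32 patients (8 per arm), and does not say which one will be enrolled

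*Combined protocol and SAP*

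**What the plan says.** All the relevant text is in the Statistical Considerations section of the combined protocol and SAP.

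- The opening sentence is about this study: "This prospective randomized control study is powered based upon prior studies our group has completed".
- The inputs are a difference of about 40% in pro-inflammatory cytokines, an SD of about 50% of baseline, alpha 0.05 and beta 0.2. The result is that "our most conservative projected sample size using a two-sided Mann-Whitney test is 25 patients per group".
- The enrolment plan follows: "With possible attrition we plan to enroll 30 patients per group". Then the total: "Therefore, across dosing we require a total of 120 patients in order to reach statistical significance".
- The text next turns to piloting: "For this trial, we are collecting data in order to pilot a larger trial after we have data from this trial". It ends with "Therefore, we expect to use the data from these 32 patients to understand how to power a larger study". The number 32 appears nowhere else and has no derivation.
- On analysis: "Patients will be used as their own controls before, during and after the exposure period, allowing for paired testing". The closing paragraph adds ANOVA of change from baseline at each time point, with significance at p<0.05.
- On allocation: "The randomization scheme will have a block size of 8. Within each block, the randomization is classic and 1:1:1:1 between groups". No total is given there.

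The official title calls the trial a pilot study.

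**The concern.** Planned enrolment is a basic design fact, and one paragraph gives it two values. The gap is too wide for attrition, since the plan's own allowance only moves 25 per group to 30. A reader cannot establish from the text how many people will be randomised, or whether the stated alpha and beta describe this trial.

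If 32 is right, the only power statement in the plan belongs to a trial that is not being run. The p<0.05 threshold nevertheless applies with nothing to mark between-dose tests as exploratory. A non-significant dose comparison could then be read as a negative result from a study with 80% power.

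**Working it through.** **Inputs from Statistical Considerations.** Difference 40%, SD 50% of baseline, two-sided alpha 0.05, beta 0.2, 25 per group before attrition, 30 after, four groups at 1:1:1:1, block size 8.

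**1. Reproducing the plan's figure.**
- Standardised effect: 0.40/0.50 = 0.8 SD.
- Normal approximation for two means: n = 2(1.96 + 0.8416)²/0.8² = 24.53, rounded up to 25 per group. This matches the plan.
- 25 to 30 per group implies an allowance of 5/30 = 16.7%; the plan states no rate.
- 30 × 4 = 120.

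The 120 is therefore a worked result. The beta of 0.2 belongs to 25 evaluable patients per group.

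**2. The second figure.**
- 32/4 = 8 per arm.
- 120 − 32 = 88; 120/32 = 3.75.
- Blocks of 8: 120/8 = 15 and 32/8 = 4. Both are complete, so block size does not discriminate.

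**3. Power at 8 per arm on the basis used for sizing** (one pair of arms, no baseline adjustment, shift 0.8 SD, two-sided 0.05).
- t-test: noncentrality 0.8 × √(8/2) = 1.6 on 14 df, power 32%.
- Exact Mann-Whitney, simulated (100,000 runs): normal 31%, logistic 34%, Laplace 40%, uniform 28%.
- Difference detectable with 80% power (t-test, 14 df): 1.51 SD, or about 75% of baseline, against the 40% assumed.
- Expected 95% CI half-width: t(0.975, 14) × √(2/8) = 1.07 SD, or about 54 percentage points.

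**4. Power at 8 per arm for the planned analyses of change.** If the 50% is a between-patient SD, the SD of change is SD × √(2(1 − r)), where r is the within-patient correlation. The document gives no r, so the values below are assumptions.

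| Analysis | r = 0 | r = 0.5 | r = 0.8 | r for 80% power |
|---|---|---|---|---|
| Pairwise contrast of changes, four-arm ANOVA, 28 df | 19% | 34% | 69% | 0.85 |
| Overall F test (3, 28 df), one arm shifted 0.8 SD | 17% | 30% | 68% | not computed |
| Within-arm paired t-test, 7 df | 28% | 50% | 86% | 0.76 |

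If the 50% instead means the SD of change itself, the r = 0.5 column applies, because √(2(1 − 0.5)) = 1.

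**5. Power if 120 is right.** The Mann-Whitney test on normal data has about 84% power if all 30 per arm complete. At 25 completers it has about 77% (81% on logistic data); the t-test has 79%.

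**The case against.** The strongest reply is that the intention can be inferred. The title says pilot, and the paragraph moves from what statistical significance would require (120) to what this trial is for, ending with 32 patients whose data will help size a larger study. On that reading, the enrolment sentence is badly placed or left over, and low between-arm power is normal in a pilot.

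Much of this stands. The pilot reading is the likelier one, and low power in a pilot is not an error in itself. But the reading has to be supplied by the reader. The sentence saying the study is powered is about this study, the 30 per group is worded as an enrolment plan, and nothing moves either to a later trial. Even if the pilot reading is right, the text needs correcting, because its power claim would then describe a different trial.

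Three smaller points:

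- The plan refers to a sample randomisation scheme in supporting documents that are not part of the file. Its length might show which total was meant, but it would not repair this section.
- The 31% is for the test used in sizing, whereas the named analyses are paired tests and ANOVA of changes. That is correct, so 31% should not be read as the power of those analyses. Their range is wide because r is unknown.
- The 25 per group comes from a formula for means, although the plan names the Mann-Whitney test. This is a minor point that does not bear on 120 versus 32.

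**Conclusion.** The concern holds. The section gives two totals for one trial, 120 and 32, 88 patients apart, and nothing in the document reconciles them.

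If enrolment is 32, the stated 80% power does not apply. For an unadjusted comparison of two arms, power is about 31% by Mann-Whitney on normal data and 32% by t-test, taking the plan's 40% difference and 50% SD at face value. For between-dose tests on change from baseline, 80% power would need a within-patient correlation of about 0.85 for a pairwise contrast. The within-arm paired test would need about 0.76. The document supports neither value.

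If enrolment is 120, the power claim is roughly right and the 32 is the error.

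**What to change.** State one enrolment figure for this trial.

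**If it is 32:** remove, or assign explicitly to the later study, the statement that this study is powered, the plan for 30 per group and the 120 needed for significance. Then add wording such as:

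> This pilot enrols 32 patients, 8 per arm, and is not powered for between-dose comparisons. For a 40% difference with SD 50%, an unadjusted pairwise Mann-Whitney test at two-sided 0.05 has about 31% power, assuming normal data. Power for change-from-baseline tests depends on a within-patient correlation not yet known. Between-dose p-values are exploratory and are reported with estimates and 95% confidence intervals.

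**If it is 120:** delete the reference to 32 patients. As a minor point, either drop the description of 25 per group as the most conservative size, or report the Mann-Whitney power at 25 and 30 completers (about 77% and 84% on normal data).

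The cost is wording only, with no extra patients. If 32 is the figure, the stated power becomes less favourable.

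### If the ANOVA of changes from baseline compares doses, it leaves out the outcome's own baseline as a covariate and probably wastes precision

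*Combined protocol and SAP*

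**What the plan says.** The last paragraph of Statistical Considerations says: "Changes from baseline will be investigated at each time point using ANOVA". It does not say whether the factor is dose or visit, and it lists no covariate. The sentence before it but one sets the allocation: "Within each block, the randomization is classic and 1:1:1:1 between groups".

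Elsewhere in the same section the analysis is within patients: "Patients will be used as their own controls before, during and after the exposure period, allowing for paired testing". Laboratory and stool results are covered only in general terms: "Changes in laboratory venous and stool samples values will be compared using parametric and non-parametric standard statistics, as required". The one dose comparison stated there is at baseline. The one covariate adjustment is for the physical tests, and it uses a risk score and comorbidities, not the earlier result of the same test: "Differences in baseline physiologic testing will be controlled for based on their RAI score and the medical comorbidities".

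Dose comparisons at follow-up are implied by the aims, for example in Study Design & Methods: "Understand the dose-specific effects of metformin on thrombotic factors, coagulation, and platelet function in an ex vivo model". Study Objectives has a similar dose-specific aim for the microbiome. No section specifies the test that would serve these aims.

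**The concern.** The ANOVA sentence takes changes at each time point, so each patient contributes one value per analysis. The obvious grouping is then the randomized arm. On that reading, baseline enters only by subtraction.

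Subtraction assumes that a patient who starts one unit higher ends one unit higher. Where the true slope is below 1, which is usual for noisy laboratory measures, subtraction adds baseline noise to the comparison. ANCOVA estimates the slope and removes only what baseline predicts. Randomization keeps both methods unbiased, so precision is what is at stake.

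With 8 patients per arm there is little precision to spare. The choice also bears on the next trial, because the plan says "we expect to use the data from these 32 patients to understand how to power a larger study". Sizing that trial well needs r, both SDs and the ANCOVA residual SD, and the plan does not undertake to report them.

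**Working it through.** **Inputs from Statistical Considerations.** Difference about 40%; SD about 50% of baseline values; two-sided alpha 0.05; power 0.80; 32 pilot patients; four arms at 1:1:1:1, so 32/4 = 8 per arm.

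**Assumptions, because the documents do not give them.** r = baseline-to-follow-up correlation, 0.3 to 0.7. k = follow-up SD / baseline SD, 0.75 to 1.5.

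**The plan's own figure.** It states "our most conservative projected sample size using a two-sided Mann-Whitney test is 25 patients per group". The normal approximation gives n = 2 × (1.960 + 0.842)² × (0.5/0.4)² = 24.5, so 25 per group, which matches. Then 25/(1 − 1/6) = 30, and 4 × 30 = 120. No correlation with baseline enters this calculation.

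**Variances, with baseline SD = 1.**

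- Change score: 1 + k² − 2rk. This equals k²(1 − r²) + (1 − rk)².
- ANCOVA: k²(1 − r²) × F, where F = (N − 5)/(N − 6) is the cost of estimating one slope with four arms. At N = 32, F = 27/26 = 1.0385.
- Share of the sample given up by the change score = 1 − ANCOVA variance / change-score variance.

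Example at k = 1, r = 0.5: change 1 + 1 − 1 = 1; ANCOVA 0.75 × 1.0385 = 0.779; share given up 22.1%.

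| k | r = 0.3 | r = 0.5 | r = 0.7 |
|---|---|---|---|
| 0.75 | 52.2% | 46.1% | 41.9% |
| 1.00 | 32.5% | 22.1% | 11.7% |
| 1.25 | 18.5% | 7.3% | −1.8% |
| 1.50 | 9.5% | −0.1% | −3.6% |

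Negative values favour the change score. At equal SDs the shares amount to about 10.4, 7.1 and 3.8 of 32 patients. Simulation of 200,000 trials with four arms of 8 agrees: 32.8% (k = 1, r = 0.3), 11.9% (k = 1, r = 0.7), 52.2% (k = 0.75, r = 0.3) and −3.6% (k = 1.5, r = 0.7).

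**When the change score wins.** Only when rk is near 1: r above 0.93 at k = 1, r from 0.65 to 0.89 at k = 1.25, r from 0.50 to 0.79 at k = 1.5, and never at k = 0.75. At rk = 1 the variance ratio is F itself, so the most ANCOVA can cost is 3.8%. If retention follows the plan's 25 of 30, 32 becomes about 27, F = 22/21, and the limit is 4.8%.

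**Power for one pairwise contrast.** This reads the 50% as the baseline SD, uses the 40% as the dose contrast, and pools the error over four arms, with 28 df for the change score and 27 for ANCOVA. The last two columns are patients per arm for 80% power in a two-arm trial. All figures are at r = 0.5.

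| k | Power, change | Power, ANCOVA | Per arm, change | Per arm, ANCOVA |
|---|---|---|---|---|
| 0.75 | 40% | 65% | 21 | 12 |
| 1.00 | 34% | 42% | 26 | 20 |
| 1.25 | 27% | 29% | 34 | 31 |
| 1.50 | 21% | 21% | 44 | 43 |

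**Cytokine response, if skewed.** Simulation of two arms of 8 (lognormal, CV 50%, 40% rise, equal log SDs), power at r = 0.3 / 0.5 / 0.7 / 0.9:

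- Mann-Whitney on raw changes: 21 / 27 / 40 / 81%
- ANCOVA on logs: 27 / 31 / 43 / 83%
- ANCOVA on ranks: 27 / 30 / 38 / 68%

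Type I error in the four-arm version was 0.046 to 0.052 for all methods.

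**The case against.** **The factor is unnamed, and the text around it is within-patient.** This stands. If the ANOVA compares visits within patients, the covariate point does not arise, so the conclusion has to be conditional. Against it, the randomization would then serve no stated test at follow-up, and the dose-specific aims would have no analysis.

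**The size is assumed.** This also stands. Neither r nor k is in the documents, and every table entry above 32.5% comes from k = 0.75. The baseline limits on HbA1c and eGFR would, if anything, push k above 1 for those two measures, where the loss shrinks or reverses. The argument for changing does not need a known r, however: the cost is capped at 3.8% with 32 patients, and the possible gain is many times larger.

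**The 50% may be the SD of the change.** The wording allows it, and the 40% comes from an ex vivo lipopolysaccharide study, not a metformin dose contrast. On that reading, change-score power would be 34% whatever r and k. This affects the power and per-arm figures, which are illustrative, but not the percentage losses.

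**The gain on the powering outcome is small.** True: about 6, 4, 3 and 2 points over Mann-Whitney. Part of that comes from the change of scale. A t-test on log changes gives 20 / 26 / 40 / 84%, so on the log scale the covariate helps at low r and adds nothing at r = 0.9.

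**The planning values can be computed whichever test is used.** Correct, and they will be imprecise. With r = 0.5 pooled within four arms, the 95% interval on the Fisher scale is 0.549 ± 1.96/√26, or about 0.16 to 0.73. That is a reason to report them with intervals.

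**The physical tests are already adjusted.** In part. The risk score and comorbidities may recover some of the loss, so the percentages above apply to an unadjusted change score. They do not replace the baseline of the same test.

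**Conclusion.** The point holds on the condition that the ANOVA compares doses. No section then enters the outcome's own baseline as a covariate, and the change score probably, though not certainly, loses precision. The loss is 11.7% to 32.5% of 32 patients at equal SDs and r = 0.3 to 0.7. Over SD ratios of 0.75 to 1.5 it runs from a 52.2% loss to a gain of at most 3.8%. These ranges rest on assumed r and k, 8 patients per arm, and a linear model.

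Nothing here biases the trial, and pairwise power is low under either method at moderate r. The recommendation rests on a cheap substitution with a bounded cost, using values that are already collected.

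**What to change.** State the factor of the ANOVA. If doses are compared, replace the sentence with wording such as:

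> For continuous outcomes, doses are compared at each time point by ANCOVA of the follow-up value (transformed where needed), with arm as factor and the baseline value of the same outcome as covariate. For grip strength and the performance battery, the baseline of the same test is added to the adjustment already planned for RAI and comorbidities. The pilot reports the baseline-to-follow-up correlation (pooled within arm), the baseline and follow-up SDs and the ANCOVA residual SD, with 95% confidence intervals, for sizing the larger study.

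If the cytokine response is skewed, fit the same model on logs. Keep ranks as the fallback, because they lose power when r is 0.7 or more. Leave the paired tests, the non-parametric route for outcomes that do not suit a linear model, and the baseline comparison of doses as they are.

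**Cost.** Analysis wording and one degree of freedom per model. The worst-case loss of precision is 3.8% with 32 patients or 4.8% with 27. For the physical tests, adding the baseline to q planned covariates costs at most (27 − q)/(26 − q) − 1: 4.0% with RAI alone and 5.0% with six covariates (the number of comorbidities is not given). Against an unadjusted change score, with RAI uninformative and equal SDs, break-even is at r = 2 × 25/27 − 1 = 0.85.
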